## 1 Introduction

We present the analysis plan executed on the data collected according to the GLORIA protocol. The analysis plan summarizes the study protocol, describes the statistical methods, data listings and summary tables for the analysis of the data from the GLORIA trial. Any differences with the original protocol will be documented.

The details of the economic evaluation and analysis of the adherence substudy will be described in a separate analysis plan.

### 1.1 Study population

The study population consists of patients of 65 years or older with rheumatoid arthritis (RA) according to the 1987 or 2010 classification criteria of the American College of Rheumatology (ACR) and the European League Against Rheumatism (EULAR) (Aletaha, 2010), requiring antirheumatic therapy because of inadequate disease control, as evidenced by a 28-joint disease activity score (DAS28) of  $\geq 2.60$ . Patients were selected from 28 hospitals in Germany, Hungary, Italy, The Netherlands, Portugal, Romania and Slovakia.

### 1.2 Study design

The GLORIA study is a randomized, double-blind, placebo-controlled pragmatic multicenter clinical trial to assess the effectiveness and safety of a daily dose of 5 mg prednisolone or matching placebo in elderly RA patients. Patients will be randomized into two arms: the experimental arm (receiving prednisolone 5 mg/day) or the control arm (receiving placebo). The trial period is 24 months with 3 additional months during which study medication treatment is tapered. In the first 3 months, co-medication is limited: co-medication can be changed only at baseline or after 3 months, creating a brief period in which the effects of prednisolone can be studied with minimum interference.

Our design emulates the routine care setting: eligibility criteria are minimal, assessments and procedures are tailored to represent standard of care, and concurrent antirheumatic treatment is allowed next to the trial medication with minimal limitations. Thus we expect that almost all elderly RA patients (specifically those with comorbidities) are eligible.

The adherence of all patients in the main GLORIA trial is monitored throughout the study period by an adherence monitoring device loaded into the cap of the drug bottle, and by a count of returned capsules at every clinic visit.

Assessment takes place at varying intervals and includes 7 clinic visits and 3 assessments by telephone. The sequence and duration of all study periods is represented in Figure 1.

**Figure 1: Schedule of assessments**

	Base-line	2 year treatment period									Follow-up / taper
		1	2	3	4	5	6	7	8	9	
Visit No	1										10
Month (visit window +/- 2 months)	0	3	6	9	12	15	18	21	24 lv	27	
Location	clinic	clinic	clinic	remote	clinic	remote	clinic	remote	clinic	clinic	
Written informed consent	X										
In- / exclusion criteria	X										
Demographics, education & medical history	X										
Baseline prognostic factors: adherence, health literacy, arthritis helplessness index	X*										
Randomization	X*										
Physical examination	X										
Height	X									X	
Vital signs / weight	X	X	X		X		X		X	X	
AE evaluation (inc. surgery, comorbidity) (safety)		X*	X*	X*	X*	X*	X*	X*	X*	X*	
Concomitant medication	X	X	X	X	X	X	X	X	X	X	
Lab (hematology  , chemistry  )	X	X	X		X		X			X	
Lab lipids 	X	X			X 					X	
Lab CRP, ESR	X	X	X		X		X		X	X	
Joint counts (44) (effectiveness)	X									X	
Joint counts (28) (effectiveness)		X	X		X		X			X	
DEXA either with VFA, or without VFA plus X-lat spine (thor, lumb) 	X									X	
X-rays hand and forefeet  (safety)	X									X	
Patient global assessment, stiffness duration, stiffness severity	X	X	X	X	X	X	X	X	X	X	
Physician global assessment	X	X	X		X		X		X	X	
Questionnaires:											
- RAID	X*	X*	X*	X*	X*	X*	X*	X*	X*	X*	
- full HAQ-DI (24 items)	X*	X*	X*		X*		X*		X*	X*	
- MHAQ-DI (10 items)				X		X		X			
- Cost questionnaire	X*	X*	X*		X*		X*		X*	X*	
- EQ-5D	X*	X*	X*	X*	X*	X*	X*	X*	X*	X*	
- SF36	X*								X*	X*	
- Patient symptom list	X*								X*	X*	
GC or placebo, dispense adherence	X*	X*	X*	X*	X*	X*	X*	X*	X*	X*	

\* procedures not belonging to standard of care

lv End of study visit. This visit also needs to be completed by subjects who early terminated the trial.

Apart from CRP and ESR, the following standard of care lab tests will be done on peripheral blood samples.

Lab results of CRP and ESR no more than 4 weeks old may be used for the baseline visit.

Results of the below tests  no more than 2 months old may be used for the baseline visit:

1) Hemoglobin, Mean Cell Volume, White blood cell count, White blood cell differential count, Platelet count.

2) Glucose (non-fasting), Creatinine, Alanine Aminotransferase;

3) Total cholesterol, HDL cholesterol. Optional for month 12.

4) For the baseline visit: DEXA, DEXA VFA and X-ray images with a maximum of 6 months before or until 3 months after the baseline visit may be used.

5) If possible a whole body DEXA may be performed.

## 1.3 Primary and secondary study objectives

### 1.3.1 Primary objectives

The primary objectives of the GLORIA project are to compare the effect of low-dose GC therapy (5 mg/day), relative to placebo, on time-averaged mean value of the disease activity *AND* the number of patients experiencing at least one AE of Special Interest for two years as co-treatment in elderly RA patients ( $\geq 65$  years).

### 1.3.2 Secondary objectives

- To assess study medication adherence through a medication packaging solution; and, in a substudy, test the effectiveness of smart device technology to improve adherence (separate statistical analysis plan, not described here).
- To assess the secondary outcome measures which are described in section 1.4.2.
- Deliver an outcome prediction model for individual patient outcome, to tailor treatment strategies for elderly RA patients with comorbidities
- Deliver data to support:
  - Better guidelines on RA treatment in elderly
  - More accurate information for elderly RA patients, their physicians and researchers
  - Improved strategies for trial design and conduct in the elderly

## 1.4 Primary and secondary endpoints

### 1.4.1 Primary endpoints

- To measure benefit, the primary endpoints are:
  - a) signs and symptoms: the time-averaged mean value (estimated from linear mixed models) of the DAS28;
  - b) damage score: change from baseline after 2-years in total Sharp/van der Heijde damage score of hands and forefeet radiographs.
- To measure safety, the primary endpoint is the total number of patients experiencing at least one adverse event of Special Interest (AESI). An AESI is defined as either a serious adverse event (SAE) according to the GCP definition, or the occurrence of one of the following AEs ('other AESI'):
  - Any AE (except loss of efficacy, worsening of disease) that leads to the definite cessation of the trial medication;
  - A cardiovascular event (myocardial infarction, cerebrovascular event, peripheral arterial vascular event);
    - Anything falling outside this definition is not an AESI. So venous hemorrhoids, venous ulcer cruris, thrombosis, pulmonary embolism, subdural hematoma, and traumatic hemorrhagic brain lesions are not coded as AESI. Also cardiac rhythm disturbances, valve lesions, cardiac insufficiency, cardiomyopathy, and encephalopathy, are not coded as AESI unless part of an acute ischemic episode.
  - Newly occurring hypertension requiring drug treatment;

- Newly occurring diabetes mellitus requiring drug treatment;
- Symptomatic bone fracture requiring treatment;
  - AESI is coded as 'no' if the vertebral fracture was asymptomatic, and 'yes' for all nonvertebral fractures, unless expressly indicated that the fracture was asymptomatic.

Note that vertebral fracture is also captured as secondary outcome through DEXA or spine radiographs.
- Infection requiring antibiotic treatment;
  - Any specific treatment aimed at microorganisms to treat an infection is included: includes topical, antiviral, antifungal, antiparasitic treatment.
  - (Surgical) procedures with concomitant antibiotics: not (initially) an infection, so not AESI; AESI only when the procedure was done for a primary infection (e.g. abscess). Surgical complications treated with antibiotics are also not coded as AESI, because it is usually impossible to determine whether the antibiotic was given as prophylaxis or as treatment.

Note: almost any surgery is of necessity (hospital admission) already an SAE.
- Newly occurring cataract or glaucoma.
  - Cataract and glaucoma are assumed to be bilateral.

A medical history of the disease in one eye counts for both, so no AESI during the trial for procedures on the contralateral eye. We count bilateral procedures for new disease as one (not two) AESI.

AEs can be reported spontaneously by patients, on prompting at clinic visits or by telephone interviews, and by the treating physician. The AEs specified above will be recorded with special care in a separate procedure. This procedure includes adjudication through the collection of evidence. This can be a declaration of the treating physician (in case of start of treatment, or a copy of a letter confirming the event, kept on file in the center).

The safety database uses the regular term and definition to describe SAE. The electronic Case Record Form and study database uses AESI to describe events that match one of the other bullets, regardless of whether the event is an SAE. So there an event can be labeled SAE (y/n) and separately AESI (y/n). In the primary analysis patients will be counted who have at least one SAE or AESI as scored in the safety database ('other AESI'), to match with the definition of primary endpoint specified above.

From here, the primary endpoint for safety is defined as 'SAE or other AESI' because one AE can be labeled as a SAE as well as an AESI.

- Cost-effectiveness and cost-utility: more details are described in the separate analysis plan for the cost analyses
- Medication adherence: adherence to trial drug is measured through the e-communicative packaging solution as the count of days in which the bottle is opened on the appropriate days, as measured by the adherence tool. The tool (cap) is collected during the study visits at 3, 6, 12, 18, 24 and 27 months. Each cap is sent back to the provider and the data are read out centrally.

## 1.4.2 Secondary endpoints

### *Benefit*

- WHO-ILAR core set of RA outcome measures, including patient and physician global assessment of disease activity, joint counts (swollen joints and tender joints), acute phase reactants (C-reactive protein (CRP) and erythrocyte sedimentation rate (ESR)) at 0, 3, 6, 12, 18, 24 and 27 months, and radiographs of hands and forefeet at 0 and 2 years.  
Remaining core set measures: pain and fatigue are part of the RAID questionnaire (see below), and physical function is assessed by the (m)HAQ.
- DAS44 – at 0 and 24 months
- DAS28 – at 3, 6, 12, 18, and 27 months
- Severity and duration of morning stiffness - at every study visit
- SF36 – The Short Form 36-item Health Survey, a questionnaire about quality of life (QoL) - at 0 and 24 months
- 57-symptom list – at 0 and 24 months
- RA Impact of Disease (RAID) tool – The RAID is a validated questionnaire assessing the seven most important domains of impact of RA on the patients: pain, functional disability assessment, fatigue, sleep, physical well-being, emotional well-being, coping. – at every study visit
- (Modified) Health Assessment Questionnaire ((m)HAQ) at every study visit
- RAPID3, calculated with the patient global assessment of disease activity, (m)HAQ and the question about pain from the RAID questionnaire, at every study visit
- Cost questionnaire at 0, 3, 6, 12, 18, 24, 27 months, including
  - Activity limitation
  - Work disability (for those holding a paid job)
- Utility/Quality-adjusted life years (QALY): Euro-QoL in 5 dimensions (EQ-5D) - at every study visit

### *Harm*

- Vital signs (heart rate and blood pressure), height, weight – at 0, 3, 6, 12, 18, 24, 27 months
- Bone mass assessed by Dual-energy X-ray Absorptiometry (DEXA) - at 0 and 24 months
- Vertebral Fracture Analysis (by DEXA OR lateral radiograph of thoracic and lumbar spine) - at 0 and 24 months
- Discontinuation of study drug with reason: this includes patients in whom treatment with prednisolone becomes clinically indicated or those with unacceptable side effects attributable to study medication
- Change of antirheumatic treatment, with reason
- Intensification of treatment for existing comorbidity, e.g. hypertension or diabetes
- Joint replacement surgery
- AEs, SAEs, other AESI at every study visit
- Concomitant medication at every study visit

Data collection is in agreement with industry standard (i.e. Meddra terminology etc.).

### *GC harm/benefit balance*

- Blood samples will be collected during the study as part of the standard of care of RA patients, of which non fasting blood samples at 0, 3, 6, 12, 18, 24 and 27 months. No additional blood samples will be taken for this study. In specific cases, extra lipid analysis will be performed on the blood samples collected as part of the standard of care.

*Medication adherence*

- Adherence to the trial drug is measured through the e-communicative packaging solution as the count of days in which the bottle is opened on the appropriate days (pill count), as measured by the adherence tool at 3, 6, 12, 18, 24 and 27 months

*Other*

- Demographics, education and medical history – at baseline
- Baseline prognostic factors: Morisky medication adherence scale (MMAS-8), health literacy, arthritis helplessness index questionnaires – at baseline
- Cost-effectiveness and cost-utility: estimate of costs of treatment and monitoring
- Patients retained on study drug over time: survival analysis

## 2 Analysis populations

For the full trial period, we will perform analyses of the primary and secondary outcome variables on the intent-to-treat (ITT) population, with ad-hoc sensitivity analyses excluding selected patients based on blinded data review. The ITT principle asserts the effect of a treatment policy (that is, the planned treatment regimen), rather than the actual treatment given (i.e., it is independent of treatment adherence etc.). Accordingly, participants allocated to a treatment group (GC and placebo, respectively) should be followed up, assessed and analysed as members of that group, irrespective of their adherence to the planned course of treatment (i.e., independent of withdrawals and cross-over phenomena). Primary safety analyses will be repeated in the safety (SAF) population.

### 2.1 Intent-to-treat population

The intent-to-treat population is defined for efficacy as all patients randomized into the study who took the study medication (prednisolone or placebo) for at least one day and who have at least one baseline and one follow-up assessment. Patients will be analyzed in the group they were randomized to.

### 2.2 Per-protocol population, also excluding initial changes in antirheumatic medication

For the 3-month efficacy assessment: this population consists of all patients who during the first 3 months:

- received the study drug;
- had at least 80% adherence to treatment as determined by tablet count;
- completed the baseline and 3-month visit;
- have a DAS28ESR value available on both visits; or a DAS28CRP value on both visits;
- did not start, stop or change the dose of concurrent antirheumatic drugs, or receive glucocorticoid (oral or injection) at baseline or in the period up to the 3-month visit;
- did not have any serious protocol violations as determined in section 3.

The report from the blinded data review and the list of patients excluded from this population have finalized before the database is locked and are attached to this plan (appendix C).

### 2.3 Safety population

All patients who took at least one capsule of study medication belong to the safety population.

## 3 Blinded review of the data

Multiple blinded data review meetings with the principal investigator, medical monitor, study lead, trial statistician, a representative of data management and a member of the scientific advisory committee will be held before breaking the blind. During the blinded data review the protocol violations and their impact on the study outcomes will be discussed. The decisions taken during the blinded data review will be finalized and signed by the participants of this meeting before breaking the blind. The final report of these meetings are attached as appendix C.

## 4 Statistical and analytical methods

### 4.1 General statistical considerations

All continuous variables will be summarized with the following descriptive statistics: number of patients (n), mean, standard deviation (SD). If the data are non-normally distributed, median, minimum (min.) and maximum (max.) will be reported. For categorical variables, the absolute (N) and relative frequency (%) will be reported.

### 4.2 Missing data handling

*Handling of missing DAS28 (disease activity) outcomes (applies to DAS28-ESR and DAS28-CRP)*

*Step 1. Imputation of missing DAS28 if only the component 'patient global assessment of disease activity' is missing*

If the missing DAS28 score is from an intermediate (i.e. not baseline or end) visit and only the patient global assessment of disease activity is missing, it will be replaced by the mean of the patient global score immediately before and after this visit, and the DAS28 score will be calculated with this result. If one or both of these are also missing the value will remain missing because we have no information to impute a value.

*Step 2. All remaining missing DAS28*

In principle, DAS28 outcomes may be incomplete for two reasons:

1. Non-monotone missingness, for example because a patient skips a clinic visit/measurement occasion but is observed again at later points in time
2. Monotone missingness in case of premature discontinuation of study medication

For the primary analysis, we use single imputation by chained equations using the MICE package (van Buuren 2012) to impute missing values according to the following rules. At each study time point we observe or do not observe patient's DAS28, DAS28-CRP, and RAPID-3 score. We impute missing values on these variables per measurement occasion, if at least one measurement is present. If all three measurements are missing, we do not impute any value. These cases usually occur due to discontinuation of the study. The main analysis model (section 4.10) is a mixed effects longitudinal model which gives consistent estimates under the assumption that the remaining missing DAS28 outcomes are missing at random (Little and Rubin 2002).

*Sensitivity analysis: Nonresponder imputation*

Finally, in case of monotone missingness we investigate the possibility that the missingness occurs not at random (NMAR) with robustness analyses (nonresponder imputation). This imputation method recodes the outcomes of all complete units observed at the end of the study period (j=m),  $Y_m$ , as follows:

$$\tilde{Y}_m = \begin{cases} 1 & \text{iff } Y_m - Y_1 < -0.6 \\ 0 & \text{iff } Y_m - Y_1 \geq -0.6 \end{cases}$$

where 0.6 denotes a minimum effect. Incomplete units receive  $\tilde{Y}_m = 0$  representing the conservative hypothesis that all incomplete cases would not have achieved a minimum treatment effect.

Subsequently, we test whether the proportions of responders ( $\tilde{Y}_m = 1$ ) differs significantly between treatment and placebo with a model for difference in proportions akin to model 3 in section 3.3.

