##### *Step 2. All remaining missing damage assessments*

We may distinguish three missing data patterns in the damage scores at study onset and study endpoint:

1. Damage score is not observed at study onset but the endpoint is observed,
2. Damage score is observed at study onset but the endpoint is unobserved,
3. Damage score is neither observed at study onset nor endpoint.

The three missing data patterns are addressed as follows.

For the primary analysis, we use the algorithm 'MICE' (multiple imputation by chained equations) to impute missing measurements (van Buuren, 2012). This procedure assumes missing at random (MAR) data. The imputation models use data available at baseline (damage score at baseline, disease duration, rheumatoid factor positivity, ACPA positivity, DAS28-ESR) and the endpoint measurement of damage. Study center is not taken into account in this imputation model in view of the large number of cases with missing endpoints.

As a sensitivity analysis, we conduct a complete case analysis deleting all cases with (remaining) missing onset outcomes or missing endpoint outcomes list-wise. This analysis thus excludes cases with patterns 1, 2 and 3. This analysis assumes these outcomes are missing completely at random, MCAR (Little & Rubin, 2002).

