#### 4.10.1.1 Full model

We model the treatment outcome by a mixed effect model with fixed effects measurement occasion after baseline (d), baseline measurement (Z), treatment condition (T), and random effects across individuals (level 2; random intercept U) and study centers (level 3; random intercept V).

Furthermore, we include the strata of the GLORIA trial (S) as fixed effects. Centers could also be modeled as fixed effects, but we have chosen random effects because several centers have included only a very low number of patients. A compound symmetry correlation structure is assumed.

We write down mixed effect model 1 as:

$$\begin{aligned}
 Y_{ijk} &= \beta_{0jk} + \sum_{s=1}^4 \beta_{1jks} d_{ijks} + \epsilon_{ijk} && \text{(level-1 model)} \\
 \beta_{0jk} &= \delta_{00k} + \delta_{01k} S_{jk1} + \delta_{02k} S_{jk2} + \delta_{03k} T_{jk} + \delta_{04k} Z_{jk} + U_{0jk} && \text{(level-2 model for intercept)} \\
 \beta_{1jks} &= \delta_{10ks} && \text{(level-2 model for slope)} \\
 \delta_{00k} &= \gamma_{000} + V_{00k} && \text{(level-3 model for intercept)} \\
 \delta_{01k} &= \gamma_{010} && \text{(level-3 model for slope)} \\
 \delta_{02k} &= \gamma_{020} && \text{(level-3 model for slope)} \\
 \delta_{03k} &= \gamma_{030} && \text{(level-3 model for slope)} \\
 \delta_{04k} &= \gamma_{040} && \text{(level-3 model for slope)} \\
 \delta_{10ks} &= \gamma_{100s} && \text{(level-3 model for slope)}
 \end{aligned}$$

with  $U_{0jk}$  the individual-level random effect,  $V_{00k}$  the center-level random effect, and  $\epsilon_{ijk}$  the residual.

The indices:

- i= 1,..., m : fixed measurement occasion after baseline (in GLORIA, m=5)
- j= 1,...,n : individuals
- k=1,...,K : study centers (currently, K=28 in GLORIA)

The variables:

- $Y_{ijk}$  : DAS28 outcome
- $d_{ijks}$  : dummy variables encoding the five measurement occasions after baseline, s=1,..., 4
- $T_{jk}$  : treatment indicator, 0 if placebo, 1 if active (prednisolone) treatment
- $Z_{jk}$ : Baseline measurement of DAS28
- $S_{jk1}, S_{jk2}$ : Stratification factors

The parameters:

- $\gamma_{000}$ : the model intercept
- $\gamma_{010}$ : fixed effect of stratification factor 1
- $\gamma_{020}$ : fixed effect of stratification factor 2
- $\gamma_{030}$ : fixed effect of treatment
- $\gamma_{040}$ : fixed effect of baseline measurement of DAS28
- $\gamma_{100s}$ : effect of time dummy s

And the random effects :

- $U_{0jk}$  : random intercept of individual i

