- $V_{00k}$ : random intercept of study center
- $\epsilon_{ijk}$ : residual

In hypotheses 1, we test for a difference in mean DAS score across a time of 24 months between treatment and placebo. In model (1), this difference in means is estimated by parameter  $\gamma_{030}$ . For the PP analysis at 3 months, the model becomes two-level (no time) as there is only one assessment post baseline.

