#### 4.10.1.2 Testing and exploration of treatment-time interactions

The significance of all parameters in model 1 is evaluated using t-tests with Satterthwaite's method for approximating degrees of freedom (Kuznetsova, Brockhoff, and Christensen, 2017). In particular, hypothesis H1a is tested by evaluating the one-sided p-value of  $\gamma_{030}$  rejecting the one-sided null hypotheses if  $\gamma_{030} < 0$  significantly and not rejecting else. The main effect of measurement occasions across all dummy variable d is evaluated jointly by a likelihood ratio test (LRT).

After this assessment, we will explore in a secondary analysis if the interaction between treatment and measurement occasions (time) interaction is significant using a LRT. If this test is significant we will test at which measurement occasions there is a significant difference using t-tests with Bonferroni correction of the p-values.

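### SAP 4.2 Step 2 fills partly measured visits in the primary DAS28 analysis by single imputation with no stated predictors; either reading slightly distorts the effect estimate or its standard error

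*SAP*

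**What the plan says.** SAP 4.2 handles missing DAS28 in two steps. Step 1 interpolates a missing patient global score. Step 2 covers the rest: "For the primary analysis, we use single imputation by chained equations using the MICE package". Its trigger is a partly measured visit: "We impute missing values on these variables per measurement occasion, if at least one measurement is present". The variables are DAS28, DAS28-CRP and RAPID-3. Visits with none of the three stay missing and are left to the mixed model under missing at random.

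The third score is patient-reported only (SAP 1.4.2): "RAPID3, calculated with the patient global assessment of disease activity, (m)HAQ and the question about pain from the RAID questionnaire". It contains no joint count and no acute-phase reactant.

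Step 2 gives no predictor list. The damage-score part of SAP 4.2 does: "The imputation models use data available at baseline (damage score at baseline, disease duration, rheumatoid factor positivity, ACPA positivity, DAS28-ESR", together with damage at the endpoint. Treatment arm is not in that list.

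The completed data go into model 1 (SAP 4.10.1.1), with five post-baseline occasions. "A compound symmetry correlation structure is assumed". The treatment contrast is one coefficient: "In model (1), this difference in means is estimated by parameter" gamma_030. SAP 4.10.1.2 adds: "The significance of all parameters in model 1 is evaluated using t-tests". The test is one-sided at 5%.

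Protocol 11.1 names multiple imputation for discontinuation and drop-out, with every variable related to missingness in the model and at least 20 data sets pooled. The DAS28 sensitivity analysis listed in SAP 4.2 is nonresponder imputation. It dichotomises the change at the end of the study and addresses monotone missingness, not Step 2.

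**The concern.** A value imputed once and analysed as if measured can mislead in two ways, and which one applies depends on a detail the SAP leaves open.

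- **Arm not in the imputation model.** The filled value reflects the treatment effect only as far as the same-visit scores carry it, so the estimate is biased.
- **Arm in the imputation model.** The bias goes, but model 1 ignores the uncertainty of the imputation, so the reported standard error is too small.

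Step 2 also names neither the patient's baseline DAS28 nor DAS28 at other visits as predictors, although model 1 relies on both. SAP 4.12 weighs benefit against harm, so the size and interval of the DAS28 effect matter as well as the p-value.

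**Working it through.** **The plan's own figures.** The documents give no number for the imputation. The DAS28 support in protocol 6.4 and SAP 6 is a contrast of −0.52 (SE 0.13) at 3 months in another trial, with 231 and 119 patients. The implied SD is 0.13/√(1/231 + 1/119) = 1.15, and z = 0.52/0.13 = 4.0, consistent with the quoted p<0.001. With 225 per arm and a single visit, SE = 1.15 × √(2/225) = 0.109, and one-sided power is Φ(0.52/0.109 − 1.645) = 99.9%.

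**Assumptions (none is in the documents).**
- Share of visits imputed, f: 10% or 20%.
- Within-arm correlation with DAS28 at the same visit: 0.9 for DAS28-CRP, 0.55 for RAPID-3. The two scores are independent given DAS28, so they correlate at 0.9 × 0.55 = 0.495.
- RAPID-3 is present at every imputed visit, DAS28-CRP at three quarters of them. The per-protocol rule in SAP 2.2 ("have a DAS28ESR value available on both visits; or a DAS28CRP value on both visits") shows that visits with only one DAS28 version are foreseen.
- k is a score's standardised treatment effect divided by that of DAS28. If treatment acts on a score only through DAS28, k equals its correlation r.

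**Without arm.** At a visit with RAPID-3 only, the imputed value carries 0.55k of the effect. With both scores present, the standardised regression slopes are
- DAS28-CRP: (0.9 − 0.55 × 0.495)/(1 − 0.495²) = 0.831
- RAPID-3: (0.55 − 0.9 × 0.495)/(1 − 0.495²) = 0.138

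The share lost is 1 minus the share carried, and overall shrinkage is f × (0.75 × loss with both + 0.25 × loss with RAPID-3 only). A negative value means exaggeration.

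| k (DAS28-CRP, RAPID-3) | loss, both present | loss, RAPID-3 only | weighted loss | f = 10% | f = 20% |
|---|---|---|---|---|---|
| 1, 1 | 0.030 | 0.450 | 0.135 | 1.4% | 2.7% |
| 0.9, 0.55 (k = r) | 0.176 | 0.698 | 0.306 | 3.1% | 6.1% |
| 1.2, 1.2 | −0.164 | 0.340 | −0.038 | −0.4% | −0.8% |
| 1.2, 2.0 | −0.275 | −0.100 | −0.231 | −2.3% | −4.6% |

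With equal k, the bias changes sign at k = 1/(0.831 + 0.138) = 1.03 where both scores are present, and at 1/(0.75 × 0.970 + 0.25 × 0.55) = 1.16 over the assumed mix.

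Simulation (450 patients, five visits, SD 1.2, within-patient correlation 0.5, true effect −0.25, values missing completely at random, no centre or strata effects) agrees for k between r and 1: shrinkage of 1.4–3.1% at 10% and 2.6–6.0% at 20%. At 10%, −0.25 becomes −0.247 to −0.242. Coverage is 94–95% and type I error 4.4–5.2%. Power at 20% is 97.4%, against 97.0–97.3% for model 1 on observed values.

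The result depends on the mix. If DAS28-CRP is always present and k = 1, shrinkage at 10% imputed is 10% × 0.030 = 0.3%. If no imputed visit has it, with r of 0.5–0.6 and k from r to 1, shrinkage at 20% is 20% × (1 − 0.6) = 8% to 20% × (1 − 0.25) = 15%.

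**With arm.** In the assumed mix the true SE is about 3–7% above the reported SE. The implied one-sided error is Φ(−1.645/1.03) = 5.5% to Φ(−1.645/1.07) = 6.2%. Simulated values are 5.3–5.7% at 10% imputed and 5.6–6.3% at 20%. A separate simulation without the baseline covariate gave reported against true SEs of 0.0818 and 0.0879 at 10%, and 0.0798 and 0.0863 at 20%, with errors of 5.9% and 6.5%.

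**At the cited contrast.** With k = r and 20% imputed, −0.52 becomes −0.52 × (1 − 0.061) = −0.488. The single-visit power above moves only from 99.9% to Φ(0.488/0.109 − 1.645) = 99.8%.

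**The case against.** The case for leaving the text alone is substantial. Step 2 names the scores to be imputed and the trigger; it does not say that nothing else may predict them. ESR and CRP are scheduled at the same visits, so a missing DAS28 may often come with DAS28-CRP, and then the bias is a fraction of a percent to about 2%. Visits with no score at all are already handled under missing at random. Protocol 11.1 ties multiple imputation to discontinuation and drop-out, which is not quite the gap that Step 2 fills. Every input to the size is assumed.

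Most of this limits the size; it does not defend the method. Pooled multiple imputation is the protocol's only general imputation method, and the SAP uses it nowhere for DAS28. The SAP's silence on arm does not rescue the step either, because both readings have a flaw.

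Several stronger readings are tempting but unsupported:
- *Arm is left out.* The damage-score list is suggestive, but it concerns another endpoint.
- *Benefit is necessarily understated.* The direction depends on how strongly the other scores respond, which is unknown.
- *The estimate shrinks and the test is also anti-conservative.* These belong to opposite readings and cannot both apply.
- *The one-score formula f(1 − rk) applies throughout.* At 10% imputed and k = 1 it gives 10% × (0.75 × 0.10 + 0.25 × 0.45) = 1.9%, against 1.4% when both scores are used.
- *The change from the protocol is undocumented.* The readable text of SAP Appendix B covers event definitions and secondary endpoints, but parts of the appendices are missing from the copy reviewed.

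**Conclusion.** The point holds as a minor one. The primary DAS28 analysis uses one imputation where the protocol's approach was pooled multiple imputation, leaves the imputation model unspecified, and has no sensitivity analysis aimed at this step. Under the assumed correlations and mix, with k between r and 1, omitting arm shrinks the effect by about 1–3% at 10% of visits imputed and 3–6% at 20%. Including arm gives a one-sided type I error of about 5–6% and about 6%. If few visits are affected, either flaw is negligible. The one-sided benefit decision would hardly change; what is affected is the size and interval reported for the first primary benefit endpoint. Confidence is high on what the text says, and medium on size and direction, which rest on quantities the documents do not give.

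**What to change.** Amend SAP 4.2 Step 2 in one of two ways, and state the predictor list wherever imputation is kept.

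(a) Use at least 20 imputations pooled by Rubin's rules, with arm, stratification factors, baseline DAS28 and the three scores at other visits in the imputation model, in line with the protocol's approach.

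(b) Drop Step 2, fit model 1 to observed DAS28 under missing at random, and report the multiple imputation in (a) as a sensitivity analysis.

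Raising the number of imputations without arm is not enough: in the assumed mix at 20% imputed, 20 arm-free imputations shrink the effect by 5.5%, against 5.3% for one.

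The cost is SAP wording and minor programming; (b) removes a step from the primary analysis. The reported interval becomes slightly wider. At 20% imputed, the simulated reported SE is 0.068 under (a) and 0.070 under (b), against 0.063–0.065 for the arm-free single imputation and 0.067 with complete data.
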